9.3. Vital Signs

Descriptive summaries of observed values and changes from baseline will be presented for systolic

Version 1.0 | 28-Feb-2025 Page 35 of 56

blood pressure, diastolic blood pressure, heart rate, and temperature which will be measured at the following visits.

Screening Period, Baseline (Study Day 1), Week 4, Week 16, Week 28, Week 40, Week 52, Week 64 and Week 76/ET/ED.

Body weight will be summarized descriptively in the tabulations for the visits at which it will be measured.

Body Mass Index (BMI): Baseline BMI results will be used from vital sign page in EDC and post baseline BMI results will be derived using post baseline body weights at each visit and screening height. A visit wise descriptive summary and change from baseline analysis of BMI will be provided.

Formula for BMI = weight in kg/ (height in metre)².

All vital signs results will be listed.

9.4. Standard 12-lead ECG

12-lead ECGs will be performed at the following visits:

Screening Period, Baseline (Study Day 1), Week 4, Week 40, and Week 76/ET/ED.

12-lead ECG readings will be obtained using an ECG machine that automatically calculates the heart rate and measures PR interval, QRS interval, RR interval, QT interval, QTcB interval (corrected QT according to Bazett), and QTcF interval (corrected QT according to Fridericia). All scheduled ECGs should be performed after the participant has rested quietly for at least 5 minutes in a supine position.

12-lead ECGs will be performed in triplicate at Baseline (Study Day 1) and thus the triplicates will be averaged for the summaries.

The ECG results will be interpreted as 'Normal', and 'Abnormal, Not Clinically Significant (NCS)', and 'Abnormal, Clinically Significant (CS)'.

The overall assessment by treatment group will be summarized at each timepoint using number and percent of participants.

[figure not shown]
For Heart Rate (beats/min), PR interval (msec), RR Interval (msec), QRS Interval (msec), QT Interval (msec), QTcF (msec), QTcB (msec), the observed and change from baseline data will be descriptively summarized by treatment group showing the number of observations (n), mean, SD, median, minimum, and maximum value.

The number and percentage of participants having observed QT, QTcB and QTcF values that satisfy the following conditions will be summarized:

- $\leq 450 \text{ msec}$
- > 450 to < 500 msec
- \bullet > 500 msec

The number and percentage of participants having change from baseline QT, QTcB and QTcF values that satisfy the following conditions will be presented:

Version 1.0 | 28-Feb-2025 Page 36 of 56

- $\leq 0 \text{ msec}$
- > 0 to ≤ 30 msec
- $> 30 \text{ to} \le 60 \text{ msec}$
- \bullet > 60 msec

All ECG findings will be listed.

9.5. Further Safety Evaluations

9.5.1. Physical Examinations

A **complete** physical examination will include the body systems: Skin, Head, Ears, Eyes, Nose, Throat, Neck/Thyroid, Lymph Nodes, Cardiovascular, Respiratory, Abdomen, Musculoskeletal, Extremities, and Other; and it will be performed at the Screening visit only. All participants with 'Normal', 'Abnormal, Not Clinically Significant (NCS)', and 'Abnormal, Clinically Significant (CS)' physical exam (complete) findings will only be listed.

A **brief** physical examination will include the body systems: general appearance, Cardiovascular, Respiratory, Abdomen, and Other; and it will be performed at the following visits:

Baseline (Study Day 1), Week 4, Week 16, Week 28, Week 40, Week 52, Week 64 and Week 76/ET/ED.

The number and percentage of participants with 'Normal', 'Abnormal, Not Clinically Significant (NCS)', and 'Abnormal, Clinically Significant (CS)' physical exam (brief) findings will be summarized by study visits.

All brief physical examination findings will be listed.

9.5.2. Neurologic Examinations

A complete neurologic examination will be performed at the Screening visit only. All complete neurologic examination findings will only be listed.

A brief neurologic examination will include the exam categories; cranial nerves [II-XII], tone, power, deep tendon reflexes, coordination, and gait; and it will be performed at the following visits: Baseline (Study Day 1), Week 4, Week 16, Week 28, Week 40, Week 52, Week 64 and Week 76/ET/ED.

The number and percentage of participants with 'normal', 'Abnormal', and 'Not Done' neurologic exam (brief) findings will be summarized by study visits.

[figure not shown]
All brief neurologic examination findings will be listed.

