3.2.1. Safety Endpoints

The safety endpoints of this study include the following:

• Incidence of adverse events (AEs) including treatment-emergent, serious, related to study

Version 1.0 | 28-Feb-2025 Page 16 of 56

drug, and leading to withdrawal along with AEs by severity and relationship to study drug

- Mean change in clinical laboratory values from baseline to Weeks 4, 16, 28, 40, 52, 64 and 76. Shifts in the normality of clinical laboratory values from baseline to Weeks 4, 16, 28, 40, 52, 64 and 76.
- Mean change in vital signs (blood pressure [supine], temperature, pulse rate) from baseline to Weeks 4, 16, 28, 40, 52, 64 and 76.
- Mean change in body weight from baseline to Weeks 4, 16, 28, 40, 52, 64 and 76.
- Shifts in physical exam (PE) findings from baseline to Weeks 4, 16, 28, 40, 52, 64 and 76.
- Shifts in neurological exam (NE) findings from baseline to Weeks 4, 16, 28, 40, 52, 64 and 76.
- Mean change in ECG parameters from baseline to Weeks 4, 40 and 76.
- Concomitant medications/treatments usage
- Shifts in the C-SSRS from baseline to Weeks 4, 16, 28, 40, 52, 64 and 76.

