8.8. Pooling With Other Studies

Data from Protocol PTI-125-06 will be pooled with data from Protocol PTI-125-07. These pooled analyses will include data from weeks 0-52 from Protocol PTI-125-06 to match the duration of Protocol PTI-125-07. Objectives and estimands for the pooled data will mirror those in Protocol

Version 1.0 | 28-Feb-2025 Page 30 of 56

PTI-125-07. Analyses will also be similar but will include an additional categorical fixed effect of study. These pooled data will be analyzed using the co-primary and multiplicity adjusted secondary endpoints and by the subgroups defined by baseline composite severity / baseline P-tau categories.

Additional analyses may be applied to the pooled data based on the findings of the PTI-125-06 study.

9. Safety and Tolerability Analysis

All safety analyses will be performed on the safety analysis set.

Safety measures including AEs, clinical laboratory values, physical examination findings, neurologic examination findings, vital signs, ECGs, and concomitant medication usage will be summarized descriptively. No inferential statistical tests will be performed, unless otherwise specified. For quantitative variables, descriptive statistics including number of observations, mean, median, standard deviation, minimum, and maximum will be presented for observed and change from baseline values at each study visit. Qualitative variables will be summarized using counts and percentages.

For all safety and tolerability analyses, participants will be analyzed by the actual treatment and dose received and, if applicable, overall.

All safety and tolerability data will be presented in participant listings.

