14.3.5 Laboratory Data Summary Tables		

Version 1.0 | 28-Feb-2025 Page 46 of 56

[figure not shown]
[figure not shown]

Table Number	Population	Table Title/Summary
14.3.5.1.1	Safety	Summary of Laboratory Results - Serum Chemistry
14.3.5.1.2	Safety	Summary of Shift from Baseline in Serum Chemistry Results
14.3.5.2.1	Safety	Summary of Laboratory Results-Hematology
14.3.5.2.2	Safety	Summary of Shift from Baseline in Hematology Results
14.3.5.3.1	Safety	Summary of Laboratory Results -Urinalysis
14.3.5.3.2	Safety	Summary of Categorical Urinalysis Results
14.3.5.4	Safety	Summary of Stopping Criteria by Treatment
14.3.6 Other Safe	ety Data Summary Ta	ables
14.3.6.1	Safety	Summary of Vital Signs Results
14.3.6.2	Safety	Summary of Weights and BMI
14.3.7.1	Safety	Summary of Concomitant Medications
14.3.7.2	Safety	Summary of Concomitant Medications-Cognitive Enhancers Taken Prior to First Dose of Study Drug
14.3.7.3	Safety	Summary of Concomitant Medications-Cognitive Enhancers Taken Post First Dose of Study Drug
14.3.8.1	Safety	Summary of Electrocardiogram Quantitative Results
14.3.8.2	Safety	Summary of Electrocardiogram Interpretation Results
14.3.8.3	Safety	Summary of Observed Categorical ECGs
14.3.8.4	Safety	Summary of Change from Baseline Categorical ECGs
14.3.9.1	Safety	Summary of Physical Examination (Brief) Results
14.3.9.2	Safety	Summary of Neurological Examination (Brief) Results
14.3.10.1	Safety	Summary of Columbia-Suicide Severity Rating Scale (C-SSRS) Suicidal Ideation and Suicidal Behavior Experienced at Any Time Post-Treatment
14.3.10.2	Safety	Summary of Columbia-Suicide Severity Rating Scale (C-SSRS) Suicidal Ideation and Suicidal Behavior by Study Visit
14.3.10.3	Safety	Shift of Columbia-Suicide Severity Rating Scale (C-SSRS) Suicidal Ideation and Suicidal Behavior from Pre-Treatment to Post-Treatment
14.3.10.4	Safety	Shift of Columbia-Suicide Severity Rating Scale (C-SSRS) Suicidal Ideation Scores from Baseline to Treatment Period
14.3.11.1	MRI Sub-study	Summary of MRI Findings

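### SAP 3.2.1 names shifts from baseline in physical and neurological examination findings as safety endpoints, but SAP 9.5 and Table 7 plan only by-visit counts, so no planned table reports them by arm (minor).

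*SAP*

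**What the plan says.** SAP 3.2.1 (Safety Endpoints) includes two bullets on the examinations: "Shifts in physical exam (PE) findings from baseline to Weeks 4, 16, 28, 40, 52, 64 and 76" and "Shifts in neurological exam (NE) findings from baseline to Weeks 4, 16, 28, 40, 52, 64 and 76". A shift classifies the same participant at baseline and again at the visit.

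The analysis text is different. For the physical examination, SAP 9.5.1 uses three categories (normal; abnormal, not clinically significant [NCS]; abnormal, clinically significant [CS]) and says that "physical exam (brief) findings will be summarized by study visits". For the neurological examination, SAP 9.5.2 says: "The number and percentage of participants with 'normal', 'Abnormal', and 'Not Done' neurologic exam (brief) findings will be summarized by study visits". Both brief examinations are done on Day 1 and at all seven later visits, so a Baseline row is among those summarised. Both sections also say that all brief findings are listed by participant, and Table 8 carries those listings (16.2.9.1.1.2 and 16.2.9.1.2.2).

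Table 7 in SAP 13.3 has one output for each examination: 14.3.9.1, "Summary of Physical Examination (Brief) Results", and 14.3.9.2, "Summary of Neurological Examination (Brief) Results". The opening of SAP Section 9 gives the general rule: "Qualitative variables will be summarized using counts and percentages". Nothing there supplies a shift table by default.

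**The concern.** Two safety endpoints are named, and no planned table presents either of them. What the tables will show instead is how many people are abnormal at each visit. That figure mixes findings already present at entry with findings that appeared on treatment, and one participant who worsens can be offset by another who improves. For a drug meant to act on the central nervous system, change in the neurological examination is a natural thing for a safety reader to look for by arm. Followed as written, the SAP would leave that reader to assemble it from listings of a trial planned for about 1,083 participants.

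**Working it through.** The plan gives no figure on this point, so there is nothing to reproduce. The check sets the sections side by side and then asks what by-visit counts can and cannot identify.

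**Step 1. Endpoint against output.**

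| Outcome | SAP 3.2.1 | Analysis section | Table 7 |
|---|---|---|---|
| Laboratory normality | Shifts, Weeks 4 to 76 | 9.2: shift tables, baseline to Week 76/ET/ED | 14.3.5.1.2 and 14.3.5.2.2, titled as shifts |
| C-SSRS | Shifts, Weeks 4 to 76 | 9.8: two shift tables, pre- to post-treatment | 14.3.10.3 and 14.3.10.4, titled as shifts |
| Physical examination | Shifts, Weeks 4 to 76 | 9.5.1: counts by visit, listings | 14.3.9.1, a summary |
| Neurological examination | Shifts, Weeks 4 to 76 | 9.5.2: counts by visit, listings | 14.3.9.2, a summary |

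MRI findings are not in the 3.2.1 list, yet SAP 9.7 separates persistent from newly occurring abnormalities. Where the SAP intends a baseline-referenced summary, it says so. The two examinations are the exception. Table 7 gives titles only, so the layout of 14.3.9.1 and 14.3.9.2 is inferred from those titles and the text of 9.5.

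**Step 2. What by-visit counts identify.** For one arm and one visit, let

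- B = number abnormal at baseline,
- V = number abnormal at the visit,
- R = number abnormal at baseline and normal at the visit,
- M = number abnormal at baseline and not examined at the visit.

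Those abnormal at the visit are the baseline-abnormal who are still abnormal, B − R − M, plus the newly abnormal. So

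newly abnormal = V − B + R + M.

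The planned tables give B and V. They give neither R nor M, because neither can be read without cross-classifying by baseline status. If R = M = 0, subtracting the Baseline row recovers the new cases exactly. Otherwise it does not. Some M is to be expected: the study stopped early, and SAP 6.1.4 says that this creates more missing data than was anticipated.

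**Step 3. How wide the gap can be.** Given only B, V and N participants in the arm, the number newly abnormal lies between max(0, V − B) and min(V, N − B). N = 361 is the planned arm size in SAP 2.2. The documents give no abnormality rates, so the percentages below are assumptions, chosen to show a range.

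| Abnormal at baseline | Abnormal at visit | B | V | Newly abnormal, min to max | % of 361 |
|---|---|---|---|---|---|
| 10% | 10% | 36 | 36 | 0 to 36 | 0 to 10.0 |
| 20% | 25% | 72 | 90 | 18 to 90 | 5.0 to 24.9 |
| 30% | 30% | 108 | 108 | 0 to 108 | 0 to 29.9 |
| 50% | 50% | 180 | 180 | 0 to 180 | 0 to 49.9 |

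For the third row: max(0, 108 − 108) = 0 and min(108, 361 − 108) = min(108, 253) = 108. These are logical limits, not forecasts. They show that the planned tables do not determine the named endpoints.

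**Step 4. Where else the information sits.** The listings hold each participant's Day 1 and later findings, so every shift can be read there, one person at a time. Protocol 10.1 counts new clinically significant examination abnormalities among its examples of adverse events, and SAP 9.1 to 9.1.3 tabulate treatment-emergent events by arm. That route depends on the investigator's judgment, does not pick up a move from normal to abnormal NCS as such, and reports events rather than examination shifts. The neurological categories in SAP 9.5.2 carry no clinical-significance grade.

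**The case against.** The best case for the plan has three parts, and most of it stands.

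First, a reader might infer that new abnormalities cannot be separated from those present at entry at all. The documents do not support that. The listings allow it, and the abnormalities that matter most clinically should also be reported as adverse events with a baseline-referenced definition and a by-arm table. What is missing is an arm-level table of the shifts themselves.

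Second, a reader might infer a calculable loss of sensitivity by comparing arms in standard errors. Take 30% abnormal at baseline and staying so, with new abnormalities in 3% and 6% of the rest. The visit counts are then 0.30 + 0.70 × 0.03 = 32.1% and 0.30 + 0.70 × 0.06 = 34.2%, and the raw contrast looks weak. But under those same assumptions the Baseline row can be subtracted, which leaves 2.1% and 4.2%. These are exactly the new cases as a share of each arm, and the standardised difference is about 1.62 against 1.63 from a shift table. Nothing is lost unless findings resolve or people leave. SAP Section 9 also plans no inferential tests on safety data unless otherwise specified, so a comparison in standard errors is beside the point.

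Third, a reader might infer that denominators shrink selectively. SAP 6.1.4 treats the administrative termination as independent of treatment and outcome. Ordinary dropout would thin a per-visit shift table just as it thins a by-visit count. The documents give no basis for claiming selective loss.

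It is also fair to say that amending 3.2.1 would remove the mismatch. It would do so by giving up the endpoints, although the data to report them are already being collected.

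**Conclusion.** The mismatch is real and minor. SAP 3.2.1 names two shift endpoints that no planned table reports by arm, and by-visit counts cannot stand in for them once abnormalities resolve or participants leave. The consequence is confined to descriptive safety reporting: alpha, power, the efficacy analyses and data collection are untouched. The conclusion rests on the text of SAP 3.2.1, 9.5.1 and 9.5.2 and on the Table 7 titles. The percentages in the working are assumptions used only to show that the counts leave the endpoints undetermined. It does not rest on any claim about how common abnormal findings are at entry.

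**What to change.** In SAP 9.5.1 and 9.5.2, and in Table 7, add shift tables by treatment received from the Day 1 brief examination to each scheduled visit. Use Normal / Abnormal NCS / Abnormal CS for the physical examination and Normal / Abnormal for the neurological examination. State the denominator as participants examined at both baseline and that visit, and show the number not examined. A worst-post-baseline column is optional, since 3.2.1 does not ask for one. The by-visit counts can stay alongside.

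The cost is a few extra descriptive tables from data already collected. Their length depends on whether they are broken down by body system and examination category.

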9.6. Concomitant Medications

Concomitant medications will be summarized descriptively by treatment group using the number and percentage of participants by Anatomical Therapeutic Chemical class (ATC level 2) and preferred term (ATC level 4).

All "Cognitive enhancers" defined by verbatim terms: donepezil (Aricept, Adlarity), galantamine (Razadyne, Reminyl), rivastigmine (Exelon) and memantine (Namenda, Ebixa, Nemdatine) will be summarized separately. All concomitant medication data will be listed. The cognitive enhancers

Version 1.0 | 28-Feb-2025 Page 37 of 56

will be flagged in the concomitant medication listing.

9.7. **MRI**

Descriptive summaries of MRI findings will be presented by treatment group with number and percentage of participants for presence of CS MRI abnormalities, total number of MH, total number of new MH, and total number of resolved MH at the following visits. The Persistence and new occurrence of MRI abnormality will be presented by treatment group at week 40 and week 76.

Baseline, Week 40 and Week 76/ET/ED.

The descriptive analysis will be presented for those subjects who signed consent for MRI substudy.

The MRI findings will be listed.

9.8. Columbia Suicide Severity Rating Scale (C-SSRS)

The C-SSRS is routinely used to quantify the presence and severity of suicidal ideation and behavior. Both the ideation and behavior subscales are sensitive to change over time.

Two versions of the C-SSRS will be used in this study: the Baseline/Screening version and the Since Last Visit version. The Baseline/Screening version of the C-SSRS assesses lifetime suicidal ideation and behavior. The Since Last Visit version of the C-SSRS assesses suicidal thoughts or behaviors the participant may have had since the last time the C-SSRS was administered.

At the screening visit, the C-SSRS Baseline/Screening version will be administered. At all subsequent visits (Baseline, Week 4, Week 16, Week 28, Week 40, Week 52, Week 64 and Week 76/ET/ED), the C-SSRS Since Last Visit version will be administered.

The C-SSRS includes "yes" or "no" responses for assessment of suicidal ideation and behavior as well as numeric ratings for severity of ideation, if present (from 1 to 5, with 5 being the most severe). A score of 0 is assigned if no ideation is present.

Self-injurious behavior without suicidal intent is also a C-SSRS outcome (although not suicide-related) and has a binary response (yes/no).

Composite endpoints are defined below:

- Suicidal ideation: A "yes" answer at any time during treatment to any one of the five suicidal ideation questions (Categories 1-5) on the C-SSRS.
- Suicidal behavior: A "yes" answer at any time during treatment to any one of the five suicidal behavior questions (Categories 6-10) on the C-SSRS.
- Suicidal ideation or behavior: A "yes" answer at any time during treatment to any one of the ten suicidal ideation and behavior questions (Categories 1-10) on the C-SSRS.

Baseline is defined as the most severe ideation and behavior reported prior to the first dose of study drug (C-SSRS assessment date <= first dose date of study drug). Suicidality data collected on the C-SSRS will be listed for all participants. Tables will include results from the Suicidal Ideation and Suicidal Behavior sections of the C-SSRS. The number and percentage of participants with a response of "Yes" at any point as well as by study visit on the Suicidal Ideation and Suicidal Behavior items will be summarized by treatment received.

Additionally, shifts of whether participants experienced suicidal ideation, behavior, or both from

Version 1.0 | 28-Feb-2025 Page 38 of 56

pre-treatment to post-treatment will be summarized in a shift table. An additional shift table of maximum ideation from pre-treatment to post-treatment will also be provided.

All C-SSRS data will be listed.

All other safety evaluations including urine drug screen results, screening laboratory assessments, Genotyping results collected at Baseline (Study Day 1), and Follow-up Phone Call data will be listed.

10. Changes from Planned Analysis

Not Applicable.

11. Other Planned Analysis

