#### **5.3.** EXCLUSION CRITERIA

Subjects meeting any of the following criteria will be excluded from the study:

- 1. Residence in a skilled nursing facility requiring 24-hour care (Note subjects may reside in an assisted living facility if they do not need 24-hour care).
- 2. Any contraindications to study procedures (e.g., potential subjects with a pacemaker that is not "MRI friendly").
- 3. A medical condition or treatment with an anticoagulant that would interfere with a lumbar puncture for those subjects being considered for participation in the CSF biomarker assessment.
- 4. BMI < 18.5 or > 37.5
- 5. Evidence of a neurologic condition other than AD that, in the judgment of the Investigator, significantly contributes to the subject's dementia, including, but not limited to, frontotemporal dementia, dementia with Lewy bodies, Parkinson's disease, corticobasal degeneration, Creutzfeldt-Jakob disease, progressive supranuclear palsy, Huntington's disease, or normal pressure hydrocephalus.
- 6. Subjects with any current primary psychiatric diagnosis other than AD if, in the judgment of the Investigator, the psychiatric disorder or symptom is likely to confound interpretation of drug effect, affect cognitive assessment, or affect the subject's ability either to comply with study procedures or to complete the study. Patients with a history of schizophrenia or chronic psychosis are excluded.

- 7. Geriatric Depression Scale (15-item) score > 8. (Note a subject with a score > 8 may continue in screening if, in the judgment of the Investigator, the elevated score is not attributed to a major depressive episode).
- 8. Affirms suicidal ideation in response to questions number 4 or 5 in the C-SSRS during the past 3 months (i.e., "active suicidal ideation with some intent to act, without specific plan," or "active suicidal ideation with specific plan and intent") or affirms any of the questions contained in the Suicidal Behavior section of the C-SSRS as applicable during the past 12 months.
- 9. Meets DSM-V criteria for alcohol or substance use disorder within 2 years before the Screening Period.

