# 8.6. COLUMBIA-SUICIDE SEVERITY RATING SCALE (C-SSRS)

The C-SSRS is an assessment tool used to assess the lifetime suicidality of a subject (C-SSRS at baseline) as well as any new instances of suicidality (C-SSRS since last visit).

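### The two C-SSRS shift tables use the lifetime worst value as reference, so on-treatment suicidality no worse than that appears as no shift or improvement

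*SAP*

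**What the plan says.** SAP 9.8 gives the scale its own baseline rule: "Baseline is defined as the most severe ideation and behavior reported prior to the first dose of study drug". Any assessment dated up to and including the first-dose date counts, so the reference is a maximum and not the latest value.

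Two forms feed the comparison, with different look-backs:
- Screening: "The Baseline/Screening version of the C-SSRS assesses lifetime suicidal ideation and behavior".
- Day 1 and every later visit: "The Since Last Visit version of the C-SSRS assesses suicidal thoughts or behaviors the participant may have had since the last time the C-SSRS was" given. Protocol 8.6 agrees that the screening form is lifetime in scope and says that the later form is there to capture new events: "as well as any new instances of suicidality (C-SSRS since last visit").

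Two shift tables are planned. Table 14.3.10.3 reports "shifts of whether participants experienced suicidal ideation, behavior, or both from" before to after treatment. Table 14.3.10.4 covers the ideation score: "An additional shift table of maximum ideation from pre-treatment to post-treatment will also be provided". That score is 0 for no ideation and otherwise uses "numeric ratings for severity of ideation, if present (from 1 to 5, with 5 being the most severe").

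Protocol 5.3, criterion 8, excludes anyone who "Affirms suicidal ideation in response to questions number 4 or 5 in the C-SSRS during the past 3 months", and anyone with suicidal behaviour in the past 12 months. Older events, and ideation at levels 1-3 at any time, do not exclude under this criterion.

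**The concern.** A shift table should show whether a person got worse relative to their state at entry. Here the reference can be an event from decades earlier. The entry criteria make this the usual case for severe history: absent an eligibility deviation, a pre-treatment score of 4-5 or a pre-treatment behaviour comes from a remote event and does not describe the participant at randomisation.

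The shift is also the only C-SSRS measure in the list of safety endpoints in SAP 3.2.1, and Tables 14.3.10.3 and 14.3.10.4 are its only tabulations. If they label a recurrence on drug as stable or improved, a reader of the safety report may draw the wrong conclusion about within-person change.

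The tables can also disagree with another table in the same report. On-treatment ideation at level 4 or 5 is a stopping criterion (Protocol 7.1.11; SAP 9.2.1). A participant with a lifetime 5 who reports a 4 on drug would be counted in the stopping-criteria summary (Table 14.3.5.4) and shown as improved in Table 14.3.10.4.

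**Working it through.** The plan gives no figure to reproduce; the check is a count of table cells.

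**Inputs.** Let L be the lifetime maximum ideation score before dosing and T the maximum score on treatment (SAP 9.8). For a participant with a history and an on-treatment event, each runs from 1 to 5, giving 5 × 5 = 25 combinations.

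**Maximum-ideation table (14.3.10.4).**
- Worsening (T > L): the sum of (5 − L) over L = 1 to 5 is 4 + 3 + 2 + 1 + 0 = 10.
- No shift (T = L): 5.
- Improvement (T < L): the sum of (L − 1) is 0 + 1 + 2 + 3 + 4 = 10.
- Not shown as worsening: 5 + 10 = 15 of 25.

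The effect depends on the history:

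| Lifetime maximum L | On-treatment scores not shown as worsening | Scores still shown as worsening |
|---|---|---|
| 1 | 1 | 2-5 |
| 2 | 1-2 | 3-5 |
| 3 | 1-3 | 4-5 |
| 4 | 1-4 | 5 |
| 5 | 1-5 | none |

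These are counts of possible cells. They say nothing about how often each cell would be filled.

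**Category table (14.3.10.3).** With the categories ideation, behaviour and both:
- No shift: ideation to ideation, behaviour to behaviour, both to both.
- Apparent improvement: both to ideation, both to behaviour.
- A new element still shows: ideation to behaviour, ideation to both, behaviour to ideation, behaviour to both.

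**With a recent-state reference.** A participant whose history is only remote, with no recent ideation, has reference 0. Every T from 1 to 5 is then above the reference, so all 25 combinations show as worsening, against 10 under the lifetime reference.

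**Comparison with the general rule.** SAP 6.1.1 takes the last observation on or before first dose as baseline. Applied to this scale, that would be the Day 1 Since Last Visit form. Section 9.8 is the specific rule and governs, but it gives no reason for the departure.

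**The case against.** The strongest reply is that nothing is hidden. SAP 9.8 defines composite endpoints that count any positive answer during treatment regardless of history. Table 14.3.10.1 gives events at any time after treatment starts, Table 14.3.10.2 gives them by visit, Table 14.3.5.4 counts participants who meet a stopping criterion, and all C-SSRS data are listed. In a randomised trial the by-arm incidence tables carry the main comparison, and the baseline definition does not touch them. Safety is descriptive, and no decision rule uses the shift tables. All of this stands, and it keeps the point small.

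A lifetime reference also has a proper use: it identifies first-ever events. That stands too, and is why it should be kept.

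A reader might infer that the shift tables are blind to emergence in anyone with a history. The documents do not support that. Ideation above the lifetime maximum still shows as worsening, as does first behaviour after a history of ideation only. Only a lifetime 5 masks every ideation score.

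A reader might also infer that the incidence tables cannot tell on-treatment events from old ones. They can, because the later forms look back only to the previous administration. What those tables do not separate is a first-ever event from a recurrence, or a recurrence after a symptom-free period from ideation already present around entry.

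Finally, the gain from a recent reference is uneven. Eligible participants have no behaviour in the past 12 months, so the behaviour shift would largely repeat the incidence in Table 14.3.10.1. Criterion 8 names the 3-month window only for questions 4 and 5, so the documents do not confirm that recent ideation at levels 1-3 is recorded at screening. This limits the screening look-backs as a source, but not the Day 1 form.

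**Conclusion.** The point holds for the two shift tables and no further. Their reference is a lifetime worst value and their comparison is an on-treatment value, so a recurrence at or below the lifetime worst is classed as no shift or improvement. That covers 15 of the 25 ideation combinations, and all five on-treatment scores for a lifetime 5.

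The number of participants affected cannot be computed. The documents give neither the share with lifetime ideation or behaviour nor its distribution by severity, and the size of the effect for each person depends on that severity. Any headcount would rest on an outside prevalence.

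The conclusion assumes that the shift tables use the reference in SAP 9.8 as written, and that the screening form's lifetime answers enter that maximum. It is an inexpensive improvement to descriptive reporting. It does not affect efficacy, any test or the incidence of suicidality by arm.

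**What to change.** In SAP 9.8, add a version of Tables 14.3.10.3 and 14.3.10.4 whose reference is the recent state: the pre-dose Day 1 Since Last Visit form, scheduled for every participant (Protocol 7.1.4 and Appendix A), plus the past-3-month ideation and past-12-month behaviour look-backs from screening where these are in the database. If they are not, the Day 1 form alone will serve. Keep the lifetime-reference tables as the second version, titled so that a reader knows they show first-ever or worse-than-ever events.

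The cost is a few lines of SAP text and one more run of two descriptive tables. More events will be classed as new, in all arms. If the data have already been unblinded, SAP section 1 allows the tables to be added, provided that they are identified as post hoc.
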